5.6.2.1. Health Questionnaires - All Patients

The primary respondent for young children will be a parent or legal guardian. For older children, the child typically will be the respondent.

5.6.2.2. Supplemental Health Questionnaires - Age 10 and Older

The premise for this additional set of adolescent questions is that:

- a) Some interviews have not been validated in younger children and/or are not appropriate
- b) In this age group, it is expected to see Type 2 diabetes and the potential occurrence of cardiovascular disease risk factors (e.g. dyslipidemia) that may be related to health behaviors

Parents will be asked to waive their right to review answers to be provided by their children, with the assurance that appropriate referrals for care will be made according to established alert values.

5.6.2.3. Assessment of Tanner Stage - Age 8 and Older (Adopted by Steering Committee 4/29/04)

This assessment is answered more accurately by the child. Tanner stage self-assessment questionnaires will be provided for children ages 8 and older.

Girls who have reached menarche will be assigned Tanner stage 5.

Boys will continue to complete self-assessment forms until they reach Tanner stage 5.

Patients will receive this questionnaire annually until they reach Tanner stage 5.

5.7. MEDICAL RECORD MODULE

Eligible Patients: Incident Cases and a Subset of Prevalent Cases

5.7.1. Medical Record Review, Incident Cases

For incident cases, standardized medical record reviews will describe 1) characteristics related to typology, 2) clinical presentation, 3) presence of selected complications, comorbidities, and medications, 4) processes of care including health care utilization and diabetes education, and 5) Tanner staging.

Data will be collected from all provider visits (in-patient and out-patient) occurring during the window of 2 months preceding and 6 months following initial diabetes diagnosis.

Information regarding insulin use and occurrences of DKA (up to 6 months after diagnosis) may be required to establish typology (see Section 7) for a small number of incident cases.

5.7.2. Typology Medical Record Review, Subset of Prevalent Cases

For prevalent cases participating in the Laboratory component of the In-Person Visit Module and who are diabetes auto-antibodies (DAA) negative, the data abstraction for prior DAA and C-peptide results and limited clinical presentation information will be conducted if data are readily available. All available data will be documented on the Core Form for each prevalent case that is eligible for typology abstraction.

5.8. FOLLOW-UP VISITS

Eligible Patients: All Incident Cases and Prevalent Hybrid Cases

All incident cases who had an initial examination will be invited to an annual follow-up, in-person examination. Table 5.2 shows the data elements and laboratory visits that will be conducted on the first follow-up visit.

5.9. TWELVE-MONTH MAILED SURVEY

Eligible Patients: Prevalent cases and All Cases (Incident and Prevalent) with “Other Specific Diabetes Type”

For all prevalent cases responding to the Initial Patient Survey, a survey designed to update health care utilization and contact information will be mailed annually after initial data collection. For cases with “Other Specific Diabetes Type”, contact information will be updated (for local use only).

5.10. CORE INFORMATION

Eligible Patients: Incident and Prevalent Cases

In order to meet a main goal of the SEARCH study, estimation of incidence and prevalence of diabetes by diabetes type, age, sex, and race/ethnicity, it is critical to have core information related to Patient’s diabetes type and demographic information. Efforts will be made to obtain participation and complete information from all identified eligible patients. The goal for these core items is to have information that will permit the percentage of registered cases that have the four core items as “known” as high as possible.

For all prevalent cases, the SEARCH study will attempt to obtain information regarding the type of diabetes diagnosis made by the Patient’s Physician or recorded in the Patient’s medical record.

Information will also be sought to assist typology. Typology information includes height, weight, insulin use, C-peptide levels, diabetic ketoacidosis and diabetes autoantibodies (DAA). Resources available do not allow for completion of information for all SEARCH prevalent cases.

5.11. VITAL STATUS

Eligible Patients: All cases.

Vital status will be documented throughout the SEARCH study based on vital status at the time of each data collection module. If death occurs, cause of death will be documented and, if possible, a death certificate obtained.

5.12. SPECIAL CONDITIONS

5.12.1. Gestational diabetes

Defined as glucose intolerance first recognized during pregnancy. Only women with diabetes (not gestational diabetes) verified by a physician post-partum are eligible for SEARCH. Persons who are pregnant will have their In-Person Visit deferred and be encouraged to return once the pregnancy is completed. Only women with a diagnosis of diabetes validated in the non-pregnant state will be eligible for participation.

5.12.2. Other Specific Diabetes Types:

Individuals for whom there is definite, prior knowledge of a genetic defect associated with beta cell dysfunction will be invited to participate in all modules. Individuals with any Other Specific Type of diabetes will be asked to participate in the Initial Patient Survey and will be contacted annually for contact information updates.

5.13. SUMMARY OF MEASURES

Table 5-2 summarizes the measures to be taken over time for the SEARCH cohort. Note, the type of case generally will not be known until the baseline data are collected.

Table 5-2. Summary of Data Collection Measure Time Points

		Year of Data Collection	
Case Type	Data Element	Baseline	FU Year 1
INCIDENT (Except known beta cell and other diabetes types of diabetes – see below)	Initial Patient Survey	X	
	In-Person, Physical Exam	X	X
	In-Person, Questionnaires	X	X
	In-Person Lab		
	DAA	X	X
	Glucose, HbA1c, lipids	X	X
	Urine albumin & creatinine	X	X
	Storage	X	X

Case Type	Data Element	Year of Data Collection		
		Baseline	FU Year 1	
	Fasting C-peptide (< 8 years old at baseline)	X	X	
	Stimulated C-peptide (\geq 8 years old)	X	X	
	Medical Record Review/ Clinical Presentation & Utilization	X		
PREVALENT (Except known beta cell and other diabetes types of diabetes – see below)	Initial Patient Survey	X		
	In-Person, Physical Exam	X		
	In-Person, Questionnaires	X		
	In-Person, Lab			
	DAA	X		
	Glucose, HbA1c, lipids	X		
	Urine alb. & creatinine	X		
	Storage	X		
	Fasting C-peptide	X		
Follow-up Mailed Questionnaire		X		
KNOWN GENETIC B-CELL DEFECT (Incident or Prevalent)	Initial Patient Survey	X		
	In-Person, Physical Exam	X		
	In-Person, Questionnaires	X	X	
	In-Person Lab			
	DAA	X	X	
	Glucose, HbA1c, lipids	X		
	Urine albumin & creatinine	X		
	Storage	X	X	
	Fasting C-peptide (< 8 years old at baseline)	X	X	
	Stimulated C-peptide (\geq 8 years old at baseline)	X	X	
Medical Record/Core Review*	X			
OTHER DIABETES TYPES	Initial Patient Survey	X		
	Follow-up Mailed Questionnaire		X	

* This medical record review will be done for incident cases only.

Hybrid diabetes is diabetes with biochemical features of both type 1 and type 2 diabetes.

Other diabetes types refer to diabetes with a known cause such as steroid-induced diabetes – See Appendix VI for greater detail.

5.13.1. Follow-up of Stimulated C-peptide Tests in Prevalent Cases

A subset of prevalent patients, 8 years of age or older at the time of their baseline In-Person Visit, will be invited to undergo stimulated C-peptide test(s) as follows:

Table 5-3. Follow-up Fasting Stimulated C-peptide Tests in Prevalent Cases

Prevalent
▪ Untypeable*
▪ Hybrid
▪ Genetic B-cell function defect

** Positive OR Negative DAA and C-peptide ≥ 0.8 ng/ml and < 3.7 ng/ml. (-See Section 7)
Hybrid diabetes is diabetes with biochemical features of both type 1 and type 2 diabetes

SEARCH Protocol – Section 6
Recruitment and Retention
Table of Contents

6. RECRUITMENT AND RETENTION.....	2
6.1. GOAL	2
6.2. RECRUITMENT.....	2
6.2.1. Recruitment Strategies	2
6.2.1.1. Education.....	2
6.2.1.2. Brochures.....	2
6.2.1.3. Information Dissemination	2
6.2.1.4. Incentives.....	2
6.2.1.5. Patient Assistance.....	3
6.3. RETENTION.....	3
6.3.1. Retention Methods	3
6.3.2. Maintaining Contact.....	3

6. Recruitment and Retention

6.1. GOAL

The goal of this section is to provide an explanation of strategies that may be used to recruit and retain as many children and youth with diabetes to the study as possible, while assuring that participation is informed and voluntary.

6.2. RECRUITMENT

6.2.1. Recruitment Strategies

Recruitment strategies that have worked in other epidemiologic studies will be used. These include:

6.2.1.1. Education

Education of health care professionals about SEARCH including a “Dear Colleague” letter, a study brochure, one-on-one meetings with physicians and other potential collaborators; presentations and Grand Rounds to physicians, school nurses, and other healthcare professionals,

6.2.1.2. Brochures

Making study brochures available in physicians’ offices.

6.2.1.3. Information Dissemination

- Introduction of the study to potential participants in a letter signed by the patient’s physician as well as by study investigators,
- Dissemination of information about SEARCH to the community in articles describing SEARCH in participating health plan and hospital newsletters, local medical and nursing newsletters; and local chapters of diabetes associations communications (e.g., the Juvenile Diabetes Foundation for Research), and in press releases in local newspapers,

6.2.1.4. Incentives

Provision of patient/family financial incentives commensurate with the level of involvement and effort,

6.2.1.5. Patient Assistance

- Making participation convenient and easy through flexibility in clinic visit times and locations and provision of examination information including maps and information about parking,
- Provision of reminders of appointment times by mail and phone.

6.3. RETENTION

6.3.1. Retention Methods

The methods that will be used to foster retention in SEARCH are:

- A yearly newsletter which will provide information about diabetes and about the study
- Provision of periodic information about the results of SEARCH either as part of the newsletter or as a separate communication
- Provision of clinical feedback about SEARCH test results to participants and their physicians (when consent has been given)

6.3.2. Maintaining Contact

To maintain contact with participants, information on address and phone number of the youth and his/her parents will be collected at baseline. In addition, the study will gather information about addresses and phone numbers of several family members and friends outside the household who could be contacted if SEARCH is unable to reach the participants at the most recent address and phone number. Information in the tracking systems that would identify individuals will be maintained at each local site and will not be made available except for the conduct of approved research studies in accordance with local IRB regulations.

SEARCH Protocol – Section 7
Typology
Table of Contents

7. TYPOLOGY	2
7.1. GOALS.....	2
7.2. METHOD OF TYPOLOGY.....	2
7.3. DEFINITIONS OF TERMS USED FOR TYPOLOGY.....	3
7.3.1. Type 1 diabetes	3
7.3.2. Type 1A diabetes (general)	3
7.3.3. Type 1A diabetes (biochemical)	3
7.3.4. Type 2 diabetes (general)	3
7.3.5. Type 2 diabetes (biochemical)	4
7.3.6. Other specific types of diabetes	4
7.3.7. Hybrid diabetes	4
7.3.8. Gestational diabetes	4
7.3.9. Autoimmunity	4
7.3.10. Insulinopenia	4
7.4. ALGORITHMS.....	5
7.4.1. General description	5
7.4.2. Incident algorithms	6
7.4.3. Prevalent algorithms	7
7.4.4. SEARCH Algorithms	8

7. Typology

7.1. GOALS

- To develop efficient and practical approaches to classification of diabetes type for prevalent and incident cases.
- To describe and compare clinical presentation and course of type 1, type 2, and other types (or hybrids) of diabetes.

7.2. METHOD OF TYPOLOGY

Background

The report of the American Diabetes Association (ADA) Expert Committee on the Diagnosis and Classification of Diabetes Mellitus published in *Diabetes Care*³² serves as the basis of definitions of the types of diabetes used in this study. The fundamental principle of the classification scheme is that definitions of diabetes types reflect pathogenesis. As a result, diabetes autoantibodies (DAA) and C-peptide information will be collected on incident and prevalent cases as the primary method of classification in this study. However, due to gaps in knowledge of diabetes pathophysiology, heterogeneity of diabetes, and that assignment of type depends on the circumstances at diagnosis, many patients are not easily categorized or typeable. To combat these limitations, the following two approaches will be used.

- a. Participants, who, at initial evaluation, cannot be classified by pathogenic criteria, will be followed longitudinally to explore the evolution of diabetes and classification will be reassigned if etiology and pathogenesis becomes clear.
- b. At study completion, clinical characteristics identified in those participants classified based on pathophysiological characteristics of diabetes type will be used to “redefine” clinical definitions of diabetes type. These “redefined” clinical definitions will be used to re-type patients who have only clinical data available.

7.3. DEFINITIONS OF TERMS USED FOR TYPOLOGY

7.3.1. **Type 1 diabetes**

The progressive destruction of the beta cells leading to an absolute deficiency of insulin (see insulinopenia below) that results in diabetes.

Type 1 diabetes will be established if all diabetes autoantibodies (DAA – see autoimmunity below) are negative and any of the following are present:

- a. Fasting C-peptide < 0.8 ng/ml;

Or

- b. Diagnosis of diabetes was made when the subject was < 10 years of age with a weight < the 25th percentile for chronological age or BMI < 50th percentile for chronological age;

Or

- c. Duration of diabetes > 1 year and if daily administration of insulin is stopped it results in DKA.

7.3.2. **Type 1A diabetes (general)**

The autoimmune destruction of the beta cells leading to an absolute deficiency of insulin resulting in diabetes.

7.3.3. **Type 1A diabetes (biochemical)**

The presence, in plasma, of any specific diabetes autoantibody and a fasting C-peptide < 3.7 ng/ml. These markers include antibodies to glutamic acid decarboxylase (GAD), IA-2, and insulin autoantibodies (IAA) measured by radioassay and cytoplasmic islet cell antibodies measured by immunofluorescence (ICA). The frequency of the presence of immune markers decreases with increased duration of disease with only 65% of Type 1A patients having one or more positive immune markers with duration of disease of 10 years^{33,34}.

7.3.4. **Type 2 diabetes (general)**

The presence of insulin resistance (see insulin resistance) and beta cell dysfunction resulting in diabetes. Type 2 diabetes will be established if one of the following exists:

- a. Duration of diabetes > 1 year and no insulin therapy for > 1 month without an episode of diabetic ketoacidosis

Or

- b. Duration of diabetes > 6 months and never treated with insulin.

7.3.5. Type 2 diabetes (biochemical)

The presence of diabetes and insulin resistance (C-peptide \geq 3.7 ng/ml) and the absence of autoimmune markers (see autoimmunity) for type 1A diabetes.

7.3.6. Other specific types of diabetes

The presence of a disease or the administration of a drug that results in beta cell destruction or dysfunction or inhibits the action of insulin resulting in diabetes (see Appendix VI). Autoimmune destruction of the beta cells is excluded from this category.

7.3.7. Hybrid diabetes

Biochemical evidence of more than one type of diabetes.

7.3.8. Gestational diabetes

Glucose intolerance first recognized during pregnancy. Only women with diabetes (not gestational diabetes) verified by a physician post-partum are eligible for SEARCH.

7.3.9. Autoimmunity

The presence of diabetes autoantibodies (DAA) to a) glutamic acid decarboxylase (GAD), b) IA-2, c) insulin autoantibody titer (IAA) if never treated with insulin, or d) islet cell antibody by immunofluorescence. The date of determination of antibody titer will be compared to the date of diagnosis. Previously collected results of Islet cell antibody (performed by immunofluorescence) will only be used when an in-person visit with direct measurement of GAD, IA-2, and IAA is not possible.

7.3.10. Insulinopenia

A fasting plasma C-peptide < 0.8 ng/ml obtained when a patient is metabolically stable (no episodes of DKA for one month prior to obtaining any laboratory tests). This concentration of C-peptide was chosen based on the following

information: a) patients with type 1 diabetes in the Diabetes Complications and Control Trial had fasting C-peptides less than 0.6 ng/ml; b) the 5th percentile for fasting plasma C-peptide in non-diabetic, healthy adolescents in the Bogalusa Heart Study was 0.8 ng/ml; and c) in non-diabetic, healthy, Swedish individuals (age range 6-22 years), the lowest value for fasting c-peptide was 0.7 ng/ml. Early in the course of type 1 diabetes, participants may have fasting C-peptide levels in the normal range^{35,36}.

- **Insulin resistance:** a fasting plasma C-peptide concentration ≥ 3.7 ng/ml based on findings in the Bogalusa Heart Study that fasting plasma C-peptide of 3.7 ng/ml exceeded the 95th percentile in non-diabetic, healthy adolescents.

7.4. ALGORITHMS

7.4.1. General description

The prevalent and incident algorithms employ DAA, plasma C-peptide tests, and clinical presentation to assign a specific classification of a type of diabetes. The algorithms are presented to indicate how to evaluate laboratory results and clinical findings as collected in Table 5-2.

SEARCH investigators recognize that a number of participants will not be able to be classified using the initial information collected. For initially untypeable cases, information from stimulated C-peptide tests (SCP) will be used for classification. Where SCP data from the initially untypeable participants are comparable to the SCP data from type 1A and type 2 incident participants, the initially untypeable group will be classified as type 1 or type 2. In participants who cannot be classified by this method, clinical definitions of diabetes will be used to classify the participants.

Participants identified as having Other Specific Types of Diabetes (see Appendix VI) will have the specific type of diabetes recorded. SCP and DAA testing will be followed in SEARCH patients having a genetic defect in beta cell function.

SEARCH investigators recognize that new information will become available during the data collection phase of this protocol concerning the biochemical, genetic, and clinical classifications of the types of diabetes. Examples of new information that may become available include: 1) previously unrecognized DAA to identify autoimmune diabetes; 2) plasma or other markers that identify types of beta cell destruction that are presently classified as idiopathic; and 3) genes that identify specific types of diabetes (e.g., new types of MODY, type 1A, type 2). As this new information becomes available, appropriate testing may be performed

and the typology algorithm may be modified to reflect the most accurate and current methods of classifying the types of diabetes.

7.4.2. Incident algorithms

The incident algorithm will be used to establish type of diabetes for incident cases. This algorithm displays use of data collected from the In-Person Visit Module. For incident cases for whom the In-Person Visit is not available, typology will proceed using data collected from the Medical Record Module or the Core Form. (See Data Collection, Section 5, for descriptions)

Algorithm - Incident cases– Information Available from In-Person Visit

- a. Type 1A diabetes will be established if any of the three DAA (GAD, IAA, and IA-2) is positive and the fasting C-peptide is < 3.7 ng/ml.
- b. Type 2 diabetes will be established if the DAA titers are all negative and the fasting C-peptide is ≥ 3.7 ng/ml.
- c. Hybrid diabetes is established if any DAA are positive and fasting C-peptide is ≥ 3.7 ng/ml.
- d. DAA negative participants ≥ 8 years of age at their baseline examination who have a fasting C-peptide concentration < 3.7 ng/ml will undergo additional DAA and SCP testing as described in Section 5 – Data Collection. These data will be used to classify participants in the following manner.
 - i. If any subsequent DAA become positive, a classification of ‘type 1A diabetes’ will be made.
 - ii. If all subsequent DAA remain negative and one or more fasting C-peptide concentrations < 3.7 ng/ml, classification will be made in the following manner. Clinical characteristics and SCP data collected over time will be compared to the same data generated in the sub-group of the incident cases classified as type 1A or all incident cases classified as type 2 diabetes. Where the data matches these groups, a classification of type 1 or type 2 will be made.
 - iii. In remaining participants who cannot be classified by the method described in ‘ii’ (above), clinical definitions of the types of diabetes found in appendix VI will be used to classify participants as type 1 and type 2 diabetes.

- iv. The remaining participants who cannot be classified by the method described in 'iii' (above) will be classified as untypeable.

Algorithm - Incident cases – Information from In-Person Visit Not Available

Among incident cases for which the In-person Module is not available, information may be available from the Core Form and/or Medical Record review. The following information will be obtained: 1) DAA and plasma C-peptide tests and the laboratory at which these tests were performed, and 2) limited clinical data.

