5.6.1.1. Laboratory: Collection of Blood and Urine Specimens

Biochemical measures to be obtained are listed in Table 5-1.

Laboratory specimens must be obtained under conditions of metabolic stability, defined as no DKA during the previous month, except for diabetes autoantibodies that can be collected at any time after initial diagnosis

Stimulated C-peptide (mixed meal challenge): Selected Patients 8 years of age or older at the time of their baseline In-Person Visit will be invited to have a stimulated C-peptide test. A fasting C-peptide and HbA_{1c} will be obtained. Following a mixed meal (Boost) challenge, C-peptide samples will be drawn at designated intervals consistent with current science. The stimulated C-peptide test will be used as follows:

- a. To establish criterion measures for insulin production among Patients with biochemically defined diabetes. This age cut-point was selected because of potentially increased difficulty to clinically diagnose type 1 versus type 2 (or hybrid) diabetes in youth at or beyond the early pubertal stage. Furthermore, based on prior work, it is expected that almost all type 2 patients will be at least 8 years of age. Detail on the use of this information is provided in Section 7 – Typology.
- b. To observe the natural history of insulin production among type 2 diabetes cases.
- c. To observe insulin production among Patients whose diabetes type is unknown according to baseline SEARCH data collection efforts. Criterion measures will be applied to these Patients (see Section - Typology).

- d. To observe the natural history of insulin production among all incident cases and prevalent cases with hybrid diabetes.
- e. To assess insulin production in both incident and prevalent cases with previously known genetic beta cell defects.

Sample storage (repository). With the appropriate process of obtaining informed consent in accordance with local IRB requirements, biologic samples will be stored for future analyses, pending acquisition of the necessary funding. See Section 11 - Human Subjects - for further description of the sample repository.

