7.4.3. Prevalent algorithms

The prevalent algorithm is used to establish the type of diabetes for prevalent cases. This algorithm displays use of data collected from the In-Person Visit Module. For prevalent cases for whom the In-Person Visit is not available, typology will proceed using data collected from the Core Form. (See Data Collection, Section 5, for descriptions)

Algorithm - Prevalent Cases – Information Available from In-Person Visit

[figure not shown]
- a. Type 1A diabetes will be established if any of the three DAA (GAD, IAA, and IA-2) are positive and a fasting C-peptide < 0.8 ng/ml (see appendix VII).
- b. Type 1 diabetes will be established if all DAA are negative and a fasting C-peptide < 0.8 ng/ml;
- c. Type 2 diabetes will be established if *all* DAA titers are negative and a fasting C-peptide is ≥ 3.7 ng/ml.
- d. Hybrid diabetes is established if any DAA is positive and fasting C-peptide ≥ 3.7 ng/ml.
- e. DAA positive patients ≥ 8 years of age at their baseline examination who have a fasting C-peptide ≥ 0.8 ng/ml and < 3.7 ng/ml will undergo a single SCP test. These data will be used to type the participants in the following manner:
 - i. The clinical and SCP data will be compared to the same data generated in the sub-groups of the incident cases classified as type 1A, hybrid diabetes and type 2.

[figure not shown]
- ii. The clinical and SCP data will be compared to the same data generated in the prevalent cases classified as hybrid diabetes and prevalent cases that are untypeable.
- f. DAA negative patients ≥ 8 years of age at their baseline examination who have a fasting C-peptide ≥ 0.8 ng/ml and < 3.7 ng/ml will undergo a single SCP test. These data will be used to type the participants in the following manner:
- i. The SCP data will be compared to the same data generated in the sub-groups of the incident cases classified as type 1A diabetes and type 2 diabetes. When the data is comparable to the sub-groups, a classification of type 1 or type 2 will be made.
 - ii. In the remaining participants who cannot be classified by the method described in ‘i’ (above), the clinical definitions of the types of diabetes found in appendix VI will be used to classify participants as type 1 and type 2 diabetes.
 - iii. The remaining participants who cannot be classified by the method described in ‘ii’ (above) will be classified as untypeable.

Algorithm- Prevalent cases – Information Available from In-Person Visit Not Available

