Autoimmunity	
 1. cytoplasmic islet cell antibodies (ICA) 2. glutamic acid decarboxylase (GAD) 3. insulin autoantibodies 4. IA-II 	
 ▪ Plasma specimen ▪ Insulin autoantibodies must be performed within 10 days of initiation of exogenous insulin therapy or the presence of insulin autoantibodies ▪ The frequency of immune markers decreases with increased duration of disease with 65% of Type 1a persons having ≥ 1 positive immune markers with duration of disease of 10 years.
Insulinopenia	A fasting plasma c-peptide < 0.8 ng/ml	
Obtained when the person is metabolically stable – defined as no episode of DKA for 1 month prior to laboratory testing. This concentration of c-peptide was chosen for the following reasons:
 
 ▪ In the Diabetes Control and Complications Trial, type 1A patients had c-peptide < 0.6 ng/ml ▪ In the Bogalusa Heart Study, the 5th percentile for fasting plasma c-peptide concentration was 0.8 ng/ml ▪ In health, non-diabetic Swedish subjects (7 to 34 years old) the 2.5th percentile was 0.7 ng/ml
Insulin Resistance	Fasting plasma c-peptide ≥ 3.7 ng./ml	This c-peptide was chosen because, in non-diabetic, health adolescents, the 95 th percentile for fasting plasma c-peptide was ≥ 3.7 ng/ml

Other Specific Types of Diabetes

Other Specific Types of Diabetes is defined as the presence of a disease or the administration of a drug that results in beta cell destruction or dysfunction or inhibits the action of insulin resulting in diabetes. Autoimmune destruction of the beta cells is excluded from this category.

Other Specific Types of Diabetes are identified by the presence of:

- Diabetes

AND

- a well defined disease or drug that results in destruction or dysfunction of the beta cells or inhibits the action of insulin.

Specific examples are:

Genetic defects of beta cell function.

- MODY 1: HNF 4 alpha
- MODY 2: Glucokinase
- MODY 3: HNF 1 alpha
- MODY 4: Insulin Promoter Factor 1
- MODY 5: HNF 1 beta
- Mitochondrial DNA
- Other

Genetic defects in insulin action

- Type A insulin resistance
- Leprechanism
- Rabson-Mendenhall Syndrome
- Lipotrophic diabetes
- Other

Disease of the exocrine Pancreas

- Pancreatitis
- Trauma/pancreatectomy
- Neoplasia
- Cystic fibrosis
- Hemochromatosis
- Fibrocalculus pancreatectomy
- Uncommon forms of immune-mediated diabetes
- “Stiff Man” Syndrome
- Anti-insulin receptor antibodies

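### The protocol gives three incompatible rules for when a positive IAA counts as autoimmunity, so an insulin-treated youth positive only for IAA is typed or routed differently depending on the section followed

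*Protocol*

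**What the plan says.** Four places in the protocol define how IAA (insulin autoantibody) counts among the diabetes autoantibodies (DAA).

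- **7.3.9 Autoimmunity** lists "insulin autoantibody titer (IAA) if never treated with insulin".
- **Appendix VI, Table 1, Autoimmunity**, comments that "Insulin autoantibodies must be performed within 10 days of initiation of exogenous insulin therapy". The rest of that comment is garbled.
- **7.3.3 Type 1A (biochemical)** lists IAA among the qualifying markers and mentions no insulin exposure.
- **7.4.2 and 7.4.3, the two algorithms**, treat IAA like GAD and IA-2. The incident type 1A step applies when "any of the three DAA (GAD, IAA, and IA-2) is positive" and C-peptide is below 3.7 ng/ml. The prevalent step applies when "any of the three DAA (GAD, IAA, and IA-2) are positive" and C-peptide is below 0.8. The incident hybrid step reads "Hybrid diabetes is established if any DAA are positive", with C-peptide at 3.7 or above, and the prevalent one is equivalent. Incident step d.i adds: "If any subsequent DAA become positive, a classification of" type 1A follows.

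Section 7.3.1 refers the term DAA to the autoimmunity definition further down.

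**The concern.** DAA status is the first split in both algorithms. The limits in 7.3.9 and Appendix VI make sense only if a positive IAA after insulin treatment is not reliable evidence of autoimmunity. The numbered steps state neither limit, and the two limits differ from each other.

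The design makes specimens taken after insulin has started routine. Prevalent cases of 2001 are studied from April 2002 (5.1). Colorado identifies incident cases within 0–6 months of onset, and Hawaii aims for 0–3 months. Table 5-2 repeats DAA in incident cases at follow-up year 1. Insulin exposure is also possible in type 2: criterion (a) of 7.3.4 requires only a period off insulin, separately from criterion (b) for those never treated.

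Aims a, b and c in 1.2 all depend on type. Errors would also spread. Incident type 1A and type 2 cases are the reference groups for typing DAA-negative cases (7.4.2 step d.ii, 7.4.3 step f.i). Section 7.2(b) then uses biochemically typed cases to redefine the clinical definitions and re-type patients who have clinical data only.

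**Working it through.** The protocol states no figure for this point, so there is none to reproduce. The check sets the rules side by side and traces one kind of participant through them.

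**Step 1. Does a positive IAA count?**

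| Specimen | 7.3.9 | Appendix VI | 7.3.3 and numbered steps |
|---|---|---|---|
| Never treated with insulin | yes | yes | yes |
| Within 10 days of starting insulin | no | yes | yes |
| More than 10 days after starting | no | no | yes |

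The sources agree only for untreated patients.

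**Step 2. Trace.** Take a participant who is GAD negative, IA-2 negative and IAA positive, sampled more than 10 days after starting insulin.

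| Case | Fasting C-peptide (ng/ml) | IAA counted | IAA not counted |
|---|---|---|---|
| Incident | ≥ 3.7 | hybrid | type 2 |
| Incident, age ≥ 8 | < 3.7 | type 1A at once | step d: repeat DAA and stimulated C-peptide, then type 1A, type 1, type 2 or untypeable |
| Incident, age < 8 | < 3.7 | type 1A | no numbered step |
| Prevalent | ≥ 3.7 | hybrid | type 2 |
| Prevalent, age ≥ 8 | 0.8 to < 3.7 | step e | step f: type 1, type 2 or untypeable |
| Prevalent, age < 8 | 0.8 to < 3.7 | no numbered step | no numbered step |
| Prevalent | < 0.8 | type 1A | type 1 |

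Step e compares the case with the type 1A, hybrid and type 2 groups but names no resulting class. An incident case that enters step d correctly can still become type 1A under d.i if IAA is positive on a later specimen taken on insulin.

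**Step 3. Can the number be computed?** The outright moves from type 2 to hybrid would be

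N(type 2) × P(insulin-treated beyond the limit) × P(IAA the only positive antibody, given that) × P(C-peptide ≥ 3.7, given both).

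Table 6-3 gives 1,048 prevalent type 2 participants for the first term. The protocol gives none of the three probabilities, so no count follows.

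**The case against.** The strongest reply is that DAA is a defined term. Section 7.3.1 sends the reader to the autoimmunity definition, 7.3.5 does the same, and 7.3.9 carries the never-treated condition. On that reading the algorithms inherit the condition, and the bracket naming three antibodies only separates the assays run at the visit from historical islet cell antibody results. This reading is arguable, and it means the steps cannot be said plainly to reject the limit. It still does not resolve the conflict. It cannot choose between never treated and 10 days, and it leaves 7.3.3 without a limit. Section 7.3.9 itself compares the antibody date with the date of diagnosis, not with the start of insulin.

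Two stronger readings are tempting and are not supported.

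- A reader might infer that 5.6.1.1 also contradicts the limits, because specimens must be drawn under metabolic stability "except for diabetes autoantibodies that can be collected at any time after initial diagnosis". That sentence exempts autoantibodies from the condition of no recent ketoacidosis. It governs when blood may be drawn, not whether an IAA result counts. GAD and IA-2 carry no insulin limit, so drawing the panel at any time is compatible with 7.3.9.
- A reader might apply assumed rates of insulin use and antibody positivity to all 1,048 in Table 6-3 and call the product lost type 2 cases. Besides the assumed rates, that omits the C-peptide term. Only prevalent cases at 3.7 or above move outright to hybrid. Those in the middle band aged 8 or over go to step e, where type 2 is still one of the comparison groups.

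It also stands that the algorithm figures and the Appendix VII cited in 7.4.3 are not in the text at hand. An exposure condition could appear there.

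**Conclusion.** The point holds as a contradiction in the written classification rule. For an insulin-treated youth positive only for IAA, the assigned type or the route changes in every C-peptide band, except for prevalent children under 8 in the middle band, who have no numbered step either way. The consequences are unequal. Hybrid instead of type 2 at 3.7 or above, and immediate type 1A in incident cases below 3.7, bear on type-specific rates and comparisons. Type 1A instead of type 1 in prevalent cases below 0.8 matters little for a type 1 versus type 2 split.

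The number of cases is unknown. The conclusion assumes that nothing in the missing figures or Appendix VII settles the rule. It needs no outside source on insulin antibodies, because the protocol's own two limits already imply that exposure matters. Since this input opens the typology behind all three primary aims, and analysts could reasonably code it in different ways, it should be corrected before the typology is run.

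**What to change.** Reconcile 7.3.3, 7.3.9, 7.4.2, 7.4.3 and Appendix VI, together with Appendix VII and the algorithm figures, into one IAA insulin-exposure rule. Which limit applies is for the investigators to decide. State it in the type 1A and hybrid steps of both algorithms and in incident step d.i. Where a specimen does not meet it, treat IAA as not evaluable and type on GAD and IA-2.

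The cost is protocol wording and one derived variable, with three consequences to plan for:

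- Some true type 1 cases positive only for IAA will become DAA-negative.
- Children under 8 need a stated route, because steps d and f cover only ages 8 and over. This affects incident cases below 3.7 and prevalent cases from 0.8 to below 3.7; at present only the partial criteria in 7.3.1 could apply to them.
- A time limit needs an insulin start date. Table 5-1 lists insulin use in the survey and record forms but no start date, and prevalent record abstraction (5.7.2) covers only DAA-negative cases with readily available data. The date would have to be captured or derived.
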